2. STUDY TITEL

The European Geriatric Emergency Departments Registry Study (EGERS Study)

3. STUDY CODE

EuSEM

4. RESEARCHERS

Physicians of each participating center.

5. PARTICIPATING CENTRES

European Emergency Departments (EDs)

6. EVALUTED BY ETHICAL COMMITTEE

Local Ethical Committees.

7. MONITOR RESPONSABLE

Non applicable.

8. TREATMENT

Non applicable.

9. PHASE OF STUDY

Non applicable.

10. STUDY OBJETIVE

Principle Objective: Description of Epidemiologic and Age Related Characteristic of geriatric patients presenting to the ED

Secondary Objective: Determination of the prognostic and predictive values of vital sign based triage scores (REMS, MEWS and VIEWS Scores) regarding hospitalization, ICU admission and in-hospital mortality for geriatric patients presenting to ED

11. DESIGN

Prospective multicentre observational study.

12. DISEASES OF INTEREST

Non applicable.

13. OUTCOME VARIABLE

Length of stay in the ED and Length of stay in the hospital if hospitalized.

Status at 30 days: alive or dead.

14. STUDY POPULATION AND SAMPLE SIZE

Patients \geq 65 years of age those presented to EDs with any symptom

Sample is generated with consecutive patients attending to EDs during study period.

15. STUDY PERIOD

From 19th October 2020 to 16th November 2020, seven consecutive days of recruitment.

2. GENERAL INFORMATION

A. Study Identification

1. Study Code EuSEM

Title: The European Geriatric Emergency Departments Registry Study (EGERS Study).

B. Study Design

Observational study

C. Study final products

Non applicable.

D. Promoter

European Society of Emergency Medicine(EuSEM).

The EuSEM office is located at:

[name]

[name]

Belgium

E. Biological samples responsible

Non applicable.

F. Study monitors

Non applicable.

G. Researchers and Centers (recruitment still ongoing)

For countries represented in the EUSEM Research network, the country PI is the country Lead of the RN.

3. INTRODUCTION, HYPOTHESIS AND OBJECTIVES

3.1 Background

Due to improved prevention, diagnosis and treatment modalities, life expectancy worldwide has risen. The number of adults over 65 years of age who are presenting to emergency services is increasing in parallel with the prolongation of the average life expectancy (1). While geriatric presentations to emergency services comprise 40–50% of all emergency service presentations in the U.S., it has been reported that 3–23% of all emergency service presentations from various regions of the country comprise patients of 65 years of age and older (2–4). There are specific management practices for patients who are 65 years and older at emergency services due to the presence of comorbidities and the change of physiological responses to acute diseases in advanced age (1,2).

Several risk-scoring systems have been developed to define the severity class of the patient during their initial evaluation at emergency services and generally named as Early Warning Scores (5–6). Early Warning Scores (EWS) incorporate physiological measurements, which do predict outcome although the addition of other simple clinical parameters might further improve the sensitivity and specificity of these scores (7). On the other hand all these EWS are simple and easy to calculate, making their use appropriate in an emergency setting (7). Of these EWS, the Modified Early Warning Score (MEWS), and the Rapid Emergency Medicine Score (REMS) have been widely used for many years (8) and The Vital PAC Early Warning Score (VIEWS) score was recently developed for the same purpose (9, 10).

Only a few studies in the literature have evaluated risk-scoring systems for the geriatric patient group. Several studies have reported that risk-scoring systems, such as Identification of Seniors at Risk (ISAR) and Triage Risk Screening Tool (TRST), which are specifically developed for geriatric patients over 65 years who present to emergency services, are not sufficiently effective for evaluating

patients in more severe conditions (11,12). Other studies have reported that the ESI triage classification predicts the prognosis correctly in only half of the patients over 65 years of age (7,13). In another study that evaluated the MEWS for the geriatric patient group, which was calculated during the presentation in emergency services, has been stated to have a prognostic value in terms of a poor result (14).

Previously the TEDGeS (Turkish Emergency Departments Geriatric Scoring Study) pilot study was carried out and published (15,16). This study enrolled all geriatric patients (age ≥ 65 years) and carried out in 13 centers (University Hospitals, Government Education and Research Hospitals and Military Hospital ED) from different cities of Turkey.

Key findings were:

- Overall 30 % of hospitalized patients from ED are elderly patients and 30 % of these hospitalized patients were ICU hospitalizations
- In hospital mortality rate is about 6 % which is very high for general hospitalized patients
- The most common presenting symptoms are related to gastrointestinal systems and about 80 % of the cases using at least one chronic medication (22.2 % of the cases using more than 4 chronic medications)
- About 45 % of the cases final diagnosis are related to cardiovascular system and gastrointestinal system and nearly 85 % of the hospitalized cases are treated in non-surgical clinics (cardiology-pulmonology-internal medicine 65 %)
- MEWS, VIEWS and REMS scores are significantly high in hospitalized patients compared to discharged from ED and also these three scores are high in ICU hospitalized patients compared to both ward hospitalized and discharged patients.

- MEWS, VIEWS and REMS scores are significantly high in non-survivors compared to survivors.
- MEWS, VIEWS scores has higher sensitivity and specificity in terms of in-hospital mortality

These results suggest that geriatric patients not only constitute significant proportion of ED presentations but also they need more hospitalization. The predictive powers of the MEWS, VIEWS and REMS scores for hospitalization and mortality in geriatric patients those presented to ED are significantly high and might be concerned in the ED triage of these patients.

References

3.2. Study objectives

MAIN OBJETIVE

The main objective of this project will be

- To determine Epidemiologic and Age Related Characteristics of Geriatric Patients presenting to the ED across Europe.

SECONDARY OBJETIVES

- To evaluate Early Warning Scoring systems (REMS, MEWS and VIEWS Scores) and determine most suitable Geriatric Emergency Medicine Risk Score regarding hospitalization, ICU admission and in-hospital mortality for patients
- To determine the most effective triage elements that can be used to predict hospitalization of geriatric patients presented to ED

- To determine the in hospital mortality and short term mortality rates of the patients above 65 years of age presenting to the ED across Europe.
- Sub analysis of ED discharged patients versus admitted patients for characteristics, comparison to recommended care and re-ED visit.
- Comparison of European data characteristics, investigation, treatment and outcome to similar data in other part of the world.

4. STUDY DESIGN

4.1. Study Design

Prospective non interventional cohort study in European EDs.

5. SELECTION OF CASES

5.1. Setting

Hospital Emergency Departments

5.2. Population Selected

Patients \geq 65 years of age those presented to EDs with any symptom

5.3. Inclusion criteria

- ✓ Consecutive geriatric patient presenting to the ED with any symptom
- ✓ 65 years or older

5.3. Exclusion criteria

- ✓ No acceptance to participated
- ✓ End of life patients

5.4. Variables included on the study

Variables are reflected on the Case Report Form

5.5. Participation centres

Sites recruitment is still ongoing.

5.6. Sample size

- ✓ All of the patients over 65 years who had presented to emergency services due to acute medical or surgical reasons during the 7 days study period are to be included. Patients younger than 65 years of age will be excluded from the study. The patients who had been brought to emergency services after having undergone cardio pulmonary resuscitation by the emergency medical team will be also excluded from the study.
- ✓ We strive for at least 25 patients per site per study period with a complete case report form (CRF). (This number is based on our pilot study, TEDGeS - Turkish Emergency Departments Geriatric Scoring Study)
- ✓ Each participating center will have to enroll all consecutive cases.

5.7 Study period

7 consecutive days from 8:00 AM to 8:00 AM

6. TREATMENT

No modification on the selected management is required.

7. STUDY METHODOLOGY. INSTRUMENTS AND PROCEDURES

7.1. Recruitment methodology.

Consecutive geriatric patient presenting to the ED during the selected study periods.

7.2. Instruments

Case report form (CRF): Appendix 1

8. ADVERS EVENTS

No intervention on establish management is requiring.
Adverse events registry and declaration is no applicable.

9. ETHICAL ASPECTS

9.1. Ethical committees

Evaluation and acceptance of the protocol by local Ethical Committees is mandatory for each participating site.

9.2. Inform consent

Depending the local regulation, an informed consent through a document might be needed.

9.3. Confidentiality

No personal data is included on the database and all the CRF forms will be filled with 'CASTOR EDC' Clinical Data Management System, which enables secure data processes. Each center and country PI will be given a password to enter the data into CRF which will be secured and only be opened with the specific password or study managers' password.

9.4. Good practices

Study should follow any local regulation related to good practices on medical research activities.

10. LOGISTIC ASPECTS

10.1. National Coordinator

There will be one national coordinator in each participating country.
His responsibilities are:

- ✓ Select the participation centers.
- ✓ To be a link between the sites and the European PIs
- ✓ Participate on the final analysis and report.

10.2. Case report form

Appendix 1

10.3. Protocol

10.3.1. Protocol modifications

Any change in the protocol has to be accepted by the EGERS steering committee and approved by the local ethics committee.

10.3.2. Changes in the protocol during the recruitment period

No changes are accepted

10.4. Data management

CRF are completed anonymously with ‘CASTOR EDC’ Clinical Data Management System, local researchers are responsible of quality in the information collected.

10.4.1. Data collection

Promoter will provide the necessary tools (CRF) and online web access to transfer data into digital application to facilitated control and management and analysis.

10.4.2. Data quality control

Specific indicators are establishing to evaluated quality of the information basically % of missing data for each variable and % on NA data on each variable.

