11.2. Missing data

Certain crucial variables are needed to accept a CRF as a useful one.

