Appendix 1: Case Report Form

EGERS CRF

European Geriatric Emergency Departments Registry Study

Inclusion criteria: All consecutive patients aged 65 or older presenting to the Emergency

Proposed study period, 7 consecutive days from 19th October 2020 to 16th November 2020:
..... (period in which recruitment was performed)

First 3 Letters of the Country |__|__|__| Site |__|__| Patient N |__|__|__|

Day of admission: Monday Tuesday Wednesday Thursday Friday Saturday Sunday

Time of admission: 00:00-08 00 08:01-16 00 16:01-20 00 20:01-23 59

Gender: M F Age (yo) |__|__|__|

Major Presenting Complaint: (Just Check One Major Complaint)

Non-Traumatic Complaint

- Abdominal Pain**
- Agitation and Psychosis**
- The Alcoholic Patient**
- Back Pain**
- Bleeding**
- Chest Pain**
- Dizziness (Vertigo)**
- Extremity Pain and Numbness**
- Fever (Elevated Temperature)**
- Headache**
- Hypotension**
- Jaundice**
- Mental Status Change and Coma**
- Palpitations and Tachycardia**
- Rash**
- Seizure**
- Shortness of Breath**
- Syncope and Near-Syncope**
- Toxic Ingestion**
- Change in Vision**
- Weakness and Fatigue**
- Abnormal findings on examination of blood (Hyperglycemia, Anemia, etc)**
- Other Non trauma.....**
.....
.....

Traumatic Complaint

- Falls**
- Motor Vehicle Accidents**
- Pedestrian Struck**
- Burns**
- Assaults**
- Other Trauma.....**
.....
.....
.....

Presentation Symptoms and Signs:

Systolic Blood Pressure: |_____| mmHg

Temperature: |____|.____| °C

Diastolic Blood Pressure: |_____| mmHg

Respiratory rate/min: |____|

Heart Rate: |_____| bpm

Oxygen saturation (SpO2): |_____| %

Needs additional oxygen supply with nasal cannula or face mask: Yes No

Glasgow Coma Score: Eye:|__| Voice:|__| Motor: |__| **TOTAL: |__|**

Co-morbidities:

 Coronary artery disease	 Dyslipidemia Chronic
 Left Ventricular Failure	 Liver disease
 Right Ventricular Failure	 Chronic inflammatory disease
 Prior coronary revascularization (Bypass)	 Active/recent malignant tumor
 Chronic Obst. Pulm. Disease	 Anemia
 Asthma	 Dementia, Alzheimer
 Chronic renal disease wo routine dialysis	 Immunosuppression/AIDS

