 Chronic renal disease with routine dialysis	 Alcohol (> 30g/day for M and > 20 g/day for F)
 Prior stroke (Hemorrhagic or Ischemic)	 Smoking (Active or stopped within last year)
 Diabetes mellitus	 Other.....
 Hypertension

Chronic Medications:

 Beta-blockers	 Oral Antidiabetics
 Calcium antagonists	 Insulin
 ACE Inhibitors or Angiotensin II receptor blockers	 Oral Steroids
 Diuretics	 Cardiac Glycosides
 Statins	 Vit K antagonists
 Antiplatelet	 Psychiatric treatment
 NSAID or Other Analgesics	 Antidepressant
 Inhaled Beta2mimetics	 Antiepileptic
 Inhaled steroids	 Chemotherapy Drugs
 Oxygen +/- NIV at home	 Other.....

Consequence of ED Presentation:	
Final (Hospital or ED for discharged patients) Principal Diagnosis (only one diagnosis):	

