 Patient Has Home Care Service  Yes  No  Patient Has History of Falls  Yes  No  Patient Has Temporary Disorientation  Yes  No  Discharged From the Emergency Department Length of stay in ED:         (hours)  Admission to the Emergency Observation unit Length of stay in Obser. Unit:         (hours)  Admitted to Wards  Cardiology  Pneumology  Internal Medicine  Geriatrics  General Surgery  Neurosurgery  Orthopedics/Traumatology  Thorax Surgery  Cardiovascular Surgery  Other  Admitted to Intensive Care Unit  Death at ED  Death during Hospitalization	
For HOSPITALIZED PATIENTS
 
STATUS at 30 days:
 
30 days:  Alive  Death
 
If Admitted to Wards or ICU
 
 Total Length of Stay in Hospital:    (days)
 
 Total Length of Stay in Wards:    (days)
 
 Total Length of Stay in ICU:    (days)
 
 Still in Wards
 
 Still in ICU

Appendix 2

Country questionnaire

Number of ED proposed

Emergency Department Questionnaire

Institution:

Address:

Local PI:

Last name: _____ First name: _____

Phone: _____

e-mail address:

How many patients per year do you receive in your Emergency Department (ED) _____

How many patients per year do you hospitalize either in your hospital or in another hospital: _____

Total number of patients presented to your ED during the study week _____

Population served (habitants) by your ED _____

Is your ED located in a: **(check ONLY ONE BOX)**

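### The comorbidity and chronic-medication tick lists have no 'None' or 'Unknown' box, so the planned % missing and % NA cannot be derived for these two blocks

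*Combined protocol and SAP*

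**What the plan says.** Section 10.4.2 (Data quality control) names the quality indicators as, in essence, the percentage "of missing data for each variable and % on NA data on each variable".

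Appendix 1 (Case Report Form) collects two long lists as single tick boxes:

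- "Co-morbidities": 20 named conditions and habits plus Other. "Dementia, Alzheimer" is one box; "Hypertension" is the last. No 'None', 'No' or 'Unknown' box follows.
- "Chronic Medications": 19 named entries plus Other, again with no negative or unknown option.

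Other items on the form have an explicit negative answer, for example "Needs additional oxygen supply with nasal cannula or face mask: Yes No". The item "Patient Has History of Falls" has Yes and No, as do home care service and temporary disorientation.

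Section 11.2 (Missing data) says only: "Certain crucial variables are needed to accept a CRF as a useful one". It does not name those variables or say how an unticked box is treated. Section 11.1 reports categorical variables as number and percentage, with no rule for the denominator.

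**The concern.** An untouched list from a patient with no disease or no medication looks the same as one from a patient whose history nobody could obtain. The form therefore does not supply what Section 10.4.2 sets out to monitor in these blocks.

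Both lists are core content for the main objective, which is descriptive (Section 3.2). They also feed the planned sub-analysis of discharged against admitted patients. If blanks are read as absent, every unobtained history lowers the recorded prevalence and no quality indicator reveals it. Histories may be harder to obtain from patients with dementia, a low coma score or early death, so the loss may differ between the two disposition groups. Each group's prevalence is then too low, and the difference between groups can move either way.

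The distinction is lost when the form is filled in and cannot be recovered from the CRF data afterwards.

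**Working it through.** The documents give no missing-data figure to reproduce. The check is a reading of the form, followed by an illustration.

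**Step 1: can the indicators be derived?** There are two ways to code a blank box in these lists.

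- Blank = absent: % missing is 0 by construction, whatever happened at the bedside.
- Blank = missing: every true negative counts as missing.

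Neither gives the intended figure, and with no NA option printed, % NA has no source. This affects 20 + 19 = 39 named variables. For a Yes/No item a blank can be counted as missing, so % missing works there. It also works for vital signs, coma score and age.

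**Step 2: inputs for the illustration.**

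- Share on at least one chronic medication, p = 0.80: the pilot result in Section 3.1, taken at face value as the true share.
- Expected size: Section 11.3.1 gives 40 to 50 sites averaging at least 25 patients, so 40 × 25 = 1,000 to 50 × 25 = 1,250.
- Share of histories wholly unobtained, u: not in the documents. Assumed at 5%, 10% and 20%.
- Loss assumed independent of medication use, and blanks read as absent.

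**Step 3: formulas.**

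- Apparent share on at least one medication = p(1 − u)
- Blank lists = (1 − p)(1 − u) + u = 0.20 + 0.80u
- Share of blank lists that are unobtained histories = u / (0.20 + 0.80u)

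| u (assumed) | At least one medication | Blank list ('no medication') | Blank lists, n of 1,000–1,250 | Of blanks, unobtained |
|---|---|---|---|---|
| 0 | 80% | 20% | 200–250 | 0% |
| 5% | 76% | 24% | 240–300 | 21% |
| 10% | 72% | 28% | 280–350 | 36% |
| 20% | 64% | 36% | 360–450 | 56% |

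**Step 4: dropping independence.** Only loss among medication users distorts the result. If every unobtained history belonged to a user, blanks would be 0.20 + u, that is 25% at u = 5% and 40% at u = 20%. If every one belonged to a non-user, blanks would stay at 20%. The direction is fixed (never below 20%), but the size is not, and u cannot be estimated from the form. The share of wholly blank lists is only an upper bound on wholly unobtained histories.

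**The case against.** Five points can fairly be made against this.

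- **No text says a blank is coded as absent.** A reader might infer that the plan counts unobtained histories as absence of disease. The documents do not say that; it is only the usual result of a tick list. This stands, and the point on bias is conditional on it. The point on the indicators is not, since both codings fail.
- **The CASTOR screens are not shown and may hold extra options.** This is possible, but Sections 7.2 and 10.2 give Appendix 1 as the case report form, and nothing mentions further options.
- **The Yes/No items have no Unknown or NA box either.** This stands. They allow % missing but not % NA, so they are a partial contrast, not a model. Nor does it follow that quality monitoring fails across the whole form.
- **The 24–36% range rests on an assumed u and on random loss, which sits badly with the worry that loss is not random.** This stands, and the figures are illustration only. Some of the patients hardest to interview are also excluded: end-of-life patients (exclusion criteria) and those arriving after resuscitation (Section 5.6).
- **Block-level boxes give block-level indicators.** This stands. They do not detect a partly taken history, and prevalence among known blocks is unbiased only if loss is unrelated to the condition.

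A reader might also infer that country comparisons would be distorted. Section 3.2 plans a comparison of European data with other parts of the world, not between countries. The early warning scores rest on vital signs, not on these lists.

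**Conclusion.** The point holds for the two lists as printed. A blank cannot be told apart from an unobtained history, so the % missing and % NA promised in Section 10.4.2 cannot be derived for these blocks. If blanks are read as absent, the prevalences are biased downward, both overall and within the discharged and admitted groups, by an amount the data cannot show.

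The true size is unknown. The 24–36% illustration against about 20% depends on the pilot share, an assumed u of 5–20%, wholly blank lists and loss independent of medication use.

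This does not invalidate the registry and does not extend to the vital signs or scores. It is worth correcting because it touches main-objective variables, is cheap to change beforehand and cannot be repaired later from the CRF.

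**What to change.** Before recruitment starts:

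1. **Appendix 1:** add two mutually exclusive boxes to each block, 'None' and 'Unknown / history not obtainable'.
2. **CASTOR:** require at least one tick per block.
3. **Section 10.4.2:** for these lists, report % missing (block left empty) and % NA (Unknown ticked) at block level.
4. **Section 11.1:** give prevalences among patients whose block is known, and show the unknown share by site and disposition. State that these prevalences are unbiased only if loss is unrelated to the condition, and that partly taken histories remain undetected.

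If CASTOR already holds such options, stating so and showing them in Appendix 1 would settle items 1 and 2.

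**Cost:** four boxes, one edit check and a few sentences. The main burden is approval: Section 10.3.1 requires steering-committee acceptance and local ethics approval, with 40 to 50 sites expected, and Section 10.3.2 bars changes during recruitment. Form entry becomes slightly longer and prevalence denominators slightly smaller.

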10.4.3. Data

Data bases will be collected and keep under control by the EGERS steering committee. Minimum time before deleting information is five years.

10.5. Publications

Any publication has to refer to the original protocol and promoter EGERS EuSEM Research Network.

Any publication has to be communicated to National coordinators.

No use or transmission of data to a third party may be made without the prior consent of the EGERS Steering Committee

Each site will have access to its own data.

Each publication project must be submitted to the EGERS Steering Committee

10.6. Data property

Data control and property belong to the promoter: EuSEM

10.7. Author Ship

The EGERS Steering committee will be in charge of the coordination of all the articles that will be published.

The 1st author will be the one that writes the article

3 positions as authors will be dedicated to members of the EGERS Steering Committee

Position as author will also be dedicated to people who actually participated in the development of the protocol and in the drafting of the results and also the number of patients with a complete CRF.

